#### 5.2.5. Migraine Characteristics and eDiary Analysis Window

The following migraine characteristics are collected on study (i.e., on or after the randomization date) (1) before or at the time of dosing in the eDiary Migraine Report and (2)

postdose from 15 minutes through 48 hours (e.g., 15, 30, 45, 60, and 90 minutes; 2, 3, 4, 6, 8, 24 and 48 hours) in the eDiary Postdose Migraine Report:

- Pain intensity (none, mild, moderate, severe)
- MBS (nausea, phonophobia, photophobia) before dosing in the eDiary Migraine Report only
- Nausea status (present, absent)
- Nausea intensity (mild, moderate, severe), if nausea status is present
- Phonophobia status (present, absent)
- Phonophobia intensity (mild, moderate, severe), if phonophobia status is present
- Photophobia status (present, absent)
- Photophobia intensity (mild, moderate, severe), if photophobia status is present
- Functional disability level (normal, mildly impaired, severely impaired, requires bedrest)
- Aura (yes, no) preceding or accompanying headache before dosing in the eDiary Migraine Report only.

The eDiary allows participants to report one result per time point per migraine characteristics parameter.

In general, if participants answered “no” to taking study medication mistakenly already, had current pain intensity of moderate or severe before dosing, and did not use other headache medications, then the eDiary Migraine Report collects current levels of all parameters on study before dosing and at scheduled postdose time points.

Otherwise, if participants answered “yes” to taking study medication mistakenly already and provided the time of study medication taken, then the eDiary Migraine Report collects all parameters listed above (1) retrospectively at the time of dosing except MBS and aura, and (2) prospectively at scheduled postdose time points (as applicable based on study medication time).

For analyses, migraine characteristics collected in the eDiary Migraine Report are considered to be “at the time of dosing”, except MBS and aura, which is considered to be “on study before dosing”.

Windows for postdose efficacy measurements (15, 30, 45, 60, 90 minutes; 2, 3, 4, 6, 8, 24, and 48 hours) are automatically assigned by the eDiary as shown in Table 2:

**Table 2. eDiary Automated Efficacy Analysis Windows**

Postdose Evaluation	Analysis-Specified Interval	Target Time
15 minutes	10 to 20 minutes	Study medication start time + 15 minutes
30 minutes	25 to 35 minutes	Study medication start time + 30 minutes
45 minutes	40 to 50 minutes	Study medication start time + 45 minutes
60 minutes	55 to 65 minutes	Study medication start time + 60 minutes
90 minutes	85 to 95 minutes	Study medication start time + 90 minutes
2 hours	1 hour 55 minutes to 2 hours 15 minutes	Study medication start time + 2 hours
3 hours	2 hour 45 minutes to 3 hours 15 minutes	Study medication start time + 3 hours
4 hours	3 hour 45 minutes to 4 hours 15 minutes	Study medication start time + 4 hours
6 hours	5 hour 45 minutes to 6 hours 15 minutes	Study medication start time + 6 hours
8 Hours	7 hour 45 minutes to 8 hours 15 minutes	Study medication start time + 8 hours
24 hours	23 to 25 hours	Study medication start time + 24 hours
48 hours	47 to 49 hours	Study medication start time + 48 hours

### 5.3. Methods to Manage Missing Data

Missing data in analyses of binary endpoints are defined as follows:

- Non-Completer=Failure (NC=F): Participants with missing data at a single point are classified as failures. This missing data imputation method is applied to endpoints based on data from a single time point (e.g., co-primary endpoints) as the main analysis method.

- Non-Completer with missing data at more than 1 Time Point=Failure (NC1=F): Participants with missing data at >1 time point postdose in a specified time period are classified as failures. This missing data imputation method is applied to endpoints that are based on data from multiple time points (e.g., secondary endpoints of sustained pain freedom from 2 to 24 hours postdose) as the main analysis method.

In the sensitivity analysis of the co-primary endpoints, the following imputation strategies for missing data will be implemented.

#### Pain freedom at 2 hours postdose

- Multiple imputation: The main analysis is repeated using the copy from reference multiple imputation approach with m=30 imputations to impute missing pain intensity at 2 hours postdose. The fully conditional specification (FCS) method is used with a generalized logit distribution. Covariates may include country/region at randomization, sex, pain intensity at the time of dosing (moderate or severe), historical number of migraine attacks per month (< median, ≥ median), and MBS before dosing (nausea, phonophobia, or photophobia). First, intercurrent events of taking rescue medication at or before 2 hours postdose will be regarded as a failure. Next, missing response status (responder versus failure) in the 2-hour postdose analysis window is imputed for participants who are not missing any of the covariates (participants missing any of the covariates are considered failures).
- Varying response rate imputation: The main analysis is repeated by imputing missing pain intensity at 2 hours postdose in each treatment group with varying response rates over the range of 0%, 10%, 20% and 30%. First, intercurrent events of taking rescue medication at or before 2 hours postdose will be regarded as a failure (RM=F, see [Appendix 2.1](#)). Next, missing response status (responder versus failure) in the 2-hour postdose analysis window is imputed.

#### MBS freedom at 2 hours postdose

- Multiple imputation: The main analysis is repeated using the copy from reference multiple imputation approach with m=30 imputations to impute missing MBS status at 2 hours postdose analysis window. First, participants whose MBS before dosing is missing are classified as failures. Next, intercurrent events of taking rescue medication at or before 2 hours postdose will be regarded as a failure (RM=F). Finally, missing response status (responder versus failure) in the 2-hour postdose analysis window is imputed.
- Varying response rate imputation: The main analysis is repeated by imputing missing MBS at 2 hours postdose in each treatment group with varying response rates over the range of 0%, 10%, 20% and 30%. First, participants whose MBS before dosing is missing are classified as failures. Next, intercurrent events of taking rescue medication at or before 2 hours postdose will be regarded as a failure. Finally,

missing response status (responder versus failure) in the 2-hour postdose analysis window is imputed.

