##### 9.3.2.2. Sensitivity Analyses

Sensitivity analyses for co-primary endpoints include the following:

- Multiple imputation: The main analysis is repeated using a multiple imputation approach to impute missing data for a co-primary endpoint at 2 hours postdose.

Appropriate covariates may be included. First, intercurrent events of taking rescue medication at or before 2 hours postdose will be regarded as a failure. Next, missing response status (responder versus failure) in the 2-hour postdose analysis window is imputed for participants who are not missing any of the covariates (participants missing any of the covariates are considered failures). The same statistics as the main analysis are presented. The imputation details and analysis window will be described in the SAP.

- Varying response rate imputation: The main analysis is repeated by imputing missing data for a primary endpoint at 2 hours postdose in each treatment group with varying response rates over the range of 0%, 10%, 20% and 30%. First, intercurrent events of taking rescue medication at or before 2 hours postdose will be regarded as a failure. Next, missing response status (responder versus failure) in the 2-hour postdose analysis window is imputed. The imputation details and analysis window will be described in the SAP.

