### 9.5. Sample Size Determination

It is anticipated that about 90% of the 700 participants randomized to each treatment group will have a headache in the allotted time period, resulting in approximately 630 participants evaluable for efficacy in each treatment group.

The sample size calculation is based on pooled efficacy results from the Phase 2/3 BHV3500-201 and Phase 3 study BHV3500-301. The response rates for zavegepant 10 mg and for the placebo group in pooled analysis were 23.2% and 15.1%, respectively, for pain freedom at 2 hours postdose, and 40.5% and 32.1%, respectively, for MBS freedom at 2 hours postdose.

A target sample size of 1260 evaluable participants (630 per group) will provide approximately 95.7% power for the co-primary endpoint of pain freedom at 2 hours postdose, approximately 87.5% power for the co-primary endpoint of MBS freedom at 2 hours postdose, and approximately 84% power to detect a difference between treatment groups for both endpoints jointly, using a 2-sided alpha of 0.05.

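### The 0–30% imputation grid for missing MBS freedom stops below the planned placebo rate of 32.1%, and SAP 5.3 does not say whether the two arms' rates are crossed

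*SAP*

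**What the plan says.** Protocol 9.3.2.2 lists a varying response rate imputation among the sensitivity analyses for the co-primary endpoints, with missing 2-hour data imputed "in each treatment group with varying response rates over the range of 0%, 10%, 20% and 30"%. SAP 5.3 carries this over for each co-primary. For pain freedom it describes "imputing missing pain intensity at 2 hours postdose in each treatment group with varying response rates" and gives the same four values. For MBS freedom it describes "imputing missing MBS at 2 hours postdose in each treatment group with varying response rates over the range of 0%, 10%, 20% and 30"%.

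The planning rates in Protocol 9.5 (zavegepant first, then placebo) differ widely between the two endpoints: "23.2% and 15.1%, respectively, for pain freedom at 2 hours postdose", and "40.5% and 32.1%, respectively, for MBS freedom at 2 hours postdose".

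Two other rules bear on missing MBS data. The main analysis (SAP 6.1.2.1) counts a missing 2-hour MBS status as failure in both arms. The other sensitivity analysis (SAP 5.3 and 6.1.2.2) is a copy-from-reference multiple imputation.

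Neither document states how much 2-hour data is expected to be missing, or whether the imputed rates in the two arms vary independently or together.

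**The concern.** A sensitivity analysis of this kind is informative when it lets missing participants on active drug do worse, and those on placebo do better, than the main analysis assumes. For pain freedom the grid has room for this: 30% is about twice the planned placebo rate (30 / 15.1 = 1.99). For MBS freedom it does not. The highest placebo value is 2.1 points below the planned placebo rate, so no cell lets missing placebo participants do as well as planned, let alone better.

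The silence on crossing matters more. If one common rate is applied to both arms, the treatment difference hardly moves whatever the rate.

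MBS freedom is the co-primary with less planned power, and both co-primaries must succeed before any key secondary endpoint is tested. A report that the MBS result holds over the whole grid could be read as stronger evidence of robustness to missing data than the grid can supply.

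**Working it through.** **Inputs.** Rates of 40.5% and 32.1% from Protocol 9.5; "A target sample size of 1260 evaluable participants (630 per group"); "using a 2-sided alpha of 0.05"; the SAP 5.3 grid. The missing fraction m is assumed equal in both arms and varied from 1% to 15%.

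**Reproducing the plan's figures.** With unpooled variance, power = Φ(difference / SE − 1.96).
- MBS freedom: SE = √[(0.405×0.595 + 0.321×0.679)/630] = 0.02699; 0.084/0.02699 = 3.112; power = Φ(1.152) = 87.5%. Protocol 9.5 states "approximately 87.5% power for the co-primary endpoint of MBS freedom at 2 hours postdose".
- Pain freedom: 95.7%, as stated.
- Product of the two: 83.7%, against about 84% stated.

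**Model for the grid.** Let qz and qp be the imputed rates for missing zavegepant and placebo participants. The planning rates can be read in two ways, and the Protocol does not say which applies.
- Reading A, missing already counted as failure: zavegepant = 0.405 + m·qz; placebo = 0.321 + m·qp.
- Reading B, rates among participants with data: zavegepant = 0.405(1−m) + m·qz; placebo = 0.321(1−m) + m·qp.

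The test is an unstratified two-sided Wald test of the difference, 630 per arm, with imputed responders at their expected number. Country/region stratification is ignored.

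**Equal rates in both arms (reading B, m = 8%).**
- 0% in both: 0.3726 − 0.2953 = 0.0773, p = 0.0035.
- 30% in both: 0.3966 − 0.3193 = 0.0773, p = 0.0041.

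Under reading A, p stays between 0.0019 and 0.0023 for m from 5% to 15%.

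**Crossed rates.** The harshest cell is qz = 0, qp = 0.30. Worked example, reading B, m = 8%:
- zavegepant 0.405×0.92 = 0.3726
- placebo 0.321×0.92 + 0.08×0.30 = 0.3193
- difference 0.0533, SE 0.02676, z = 1.99, p = 0.047

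The tipping point below is the placebo rate at which p first exceeds 0.05 with zavegepant at 0%.

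| Missing per arm | A: p at 0%/30% | A: tipping point | B: p at 0%/30% | B: tipping point |
|---|---|---|---|---|
| 2% | 0.004 | none | 0.005 | none |
| 3% | 0.006 | none | 0.007 | 95% |
| 5% | 0.011 | 61% | 0.016 | 54% |
| 8% | 0.028 | 38% | 0.047 | 31% |
| 10% | 0.048 | 31% | 0.088 | 24% |
| 15% | 0.155 | 20% | 0.319 | 13% |

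**Thresholds.** The 0%/30% cell loses significance once m exceeds 10.2% (A) or 8.2% (B). With placebo at 100%, the threshold falls to 3.1% (A) or 2.9% (B). Between these two thresholds a tipping point exists but lies above the 30% cap.

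**The case against.** The best defence is that a crossed grid already tests the unfavourable direction. Zavegepant cannot be imputed below 0%, and the 0%/30% cell overturns the result once missingness passes about 8–10%. This stands. A reader might infer from the low cap that the grid cannot reach any unfavourable scenario; if the arms are crossed, that is wrong.

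Three related inferences also fail.
- The grid lies below the planned zavegepant rate of 40.5% as well, but that is no defect. Imputing zavegepant higher favours the drug.
- The 2.1-point gap to the planned placebo rate matters little in itself. Moving placebo from 30% to 32.1% changes the difference by 0.08 × 2.1 = 0.17 points at 8% missing. Under reading B this takes p from 0.047 to 0.054, but under reading A only from 0.028 to 0.032. At 5% missing both values are significant under either reading, so the change of verdict depends on an assumed 8% and one reading of the rates.
- The documents do not call this a worst-case or tipping-point analysis, so the plan breaks no promise of its own. The 32.1% is also a planning figure pooled from two earlier studies, not a rate observed in this trial.

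It can also be said that copy-from-reference imputation handles missing placebo participants at the placebo rate. It does, but it draws the zavegepant arm from the same distribution, so the arms move together. With both arms at 32.1% and 8% missing (reading B), p is about 0.004. It does not examine zavegepant low with placebo high.

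**Conclusion.** The point holds in a limited form. One grid serves two endpoints with very different planned rates, and for MBS freedom its upper end is too low to show the tipping point across a plausible band of missingness: about 3% to 8% per arm, or about 3% to 10% if the planning rates already count missing as failure. In that band every cell of a crossed grid would be significant. Above the band the grid does overturn the result; below it no placebo rate does. If the rates are not crossed, the analysis tests almost nothing at any missing fraction considered, so the unstated crossing is at least as important as the cap.

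These sizes rest on an assumed missing fraction equal in both arms, on the planning rates being realised, and on an unstratified test. The main analysis, the estimand and type I error control are unaffected. This is an inexpensive improvement to a sensitivity analysis, not a flaw in the primary inference.

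**What to change.** In SAP 5.3, under MBS freedom:
- State that the zavegepant and placebo imputed rates are varied independently, with all combinations reported.
- Extend the placebo rates upward until p exceeds 0.05 or 100% is reached, and report the tipping point, or that none exists. A fixed higher cap would be arbitrary, because the tipping point depends on how much is missing.

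The crossing statement should also be made for pain freedom; its 0–30% range need not change.

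The cost is a few lines of text, a longer program loop and a larger table. Keeping the four zavegepant rates and taking placebo in steps of 10 up to 100% gives at most 4 × 11 = 44 cells, against 4 × 4 = 16 for the present grid if crossed. The downside for the sponsor is a possibly less favourable robustness statement.

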## 6. ANALYSES AND SUMMARIES

### 6.1. Primary Endpoint(s)

The co-primary efficacy endpoints are as follows:

#### 6.1.1. Percentage of participants with a pain intensity of none (pain freedom) at 2 hours postdose

##### 6.1.1.1. Main Analysis

- Estimand strategy: Composite policy (Section 2.2.1).
- Analysis set: EAS (Section 4).
- Analysis methodology: The Mantel-Haenszel risk estimation stratified by country/region will be used. See details in Section 5.2.2.
- Intercurrent events and missing data: (1) Taking rescue medication at or before 2 hours postdose (RM=F; see Appendix 2.1) and (2) missing pain intensity at 2 hours postdose (NC=F; see Section 5.3 for definition) will be regarded as failures.

The following statistics are presented:

- Response rate (i.e., “n/N” and percentage), ASE, and 95% CI for each treatment group.
- Stratified percentage difference between treatment groups (zavegepant – placebo), ASE, 95% CI, and p-value.

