### **Number of Participants:**

Approximately 1400 participants will be randomized to the zavegepant or placebo treatment group in a 1:1 ratio (approximately 700 per group).

**Study Population:** Key inclusion and exclusion criteria are listed below:

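### The co-primary and key secondary comparisons do not adjust for pain or disability at dosing; adjusting would give a small gain in precision and balance and would not repair an error

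*SAP*

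**What the plan says.** SAP 6.1.1.1 sets the method for pain freedom at 2 hours: "The Mantel-Haenszel risk estimation stratified by country/region will be used". SAP 5.2.2 makes this the general method, and SAP 6.1.2.1, 6.2.1 to 6.2.8 and Appendix 1 repeat it for MBS freedom and the eight key secondary endpoints. Protocol 9.3.2.1 names the same stratification for the co-primaries.

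The predose data exist. For participants who dose as instructed, SAP 5.2.5 says that "the eDiary Migraine Report collects current levels of all parameters on study before dosing and at scheduled postdose time points". These parameters include pain intensity, symptom intensity and functional disability.

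The plan already uses some of them:
- The EAS admits only attacks that are moderate or severe at dosing (SAP 4).
- The return-to-function endpoints are restricted to participants with disability at dosing (SAP 6.2.4, 6.2.7, 6.2.8).
- The imputation model for 2-hour pain may draw on covariates including "pain intensity at the time of dosing (moderate or severe), historical number of migraine attacks per month" (SAP 5.3).
- Pain and disability at dosing are tabulated descriptively (SAP 6.5.1.3).

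No main, supportive or sensitivity analysis adjusts the treatment comparison for either variable, and neither is a subgroup variable in SAP 6.4.

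**The concern.** Restricting the EAS to moderate and severe attacks still leaves a spread of severity in the comparison. Pain relief is one step down the scale from moderate pain and at least two from severe. Normal function is one step from mildly impaired and three from requiring bedrest. A link between the predose level and response is therefore plausible, and the imputation model treats predose pain as a candidate predictor.

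Randomization cannot balance this variable. The strata are prophylactic medication use and country/region (Protocol 6.3), and the treated attack may come up to 45 days after randomization (Protocol 4.1). Only the analysis can take account of it. Both co-primaries must succeed before the key secondaries are tested, and those run in fixed sequence (SAP 5.1), so any precision gained or lost carries down the list.

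**Working it through.** **Inputs (Protocol 9.5).** The protocol expects that "about 90% of the 700 participants randomized to each treatment group will have a headache", so n = 0.9 x 700 = 630 per arm. The rates "were 23.2% and 15.1%, respectively, for pain freedom at 2 hours postdose", zavegepant first; for MBS freedom they are 40.5% and 32.1%. The test is specified "using a 2-sided alpha of 0.05".

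**Reproducing the plan's power.** SE = sqrt{[p1(1-p1) + p2(1-p2)]/n}; power = Phi(d/SE - 1.96).
- Pain freedom: SE = sqrt[(0.1782 + 0.1282)/630] = 0.02205; 0.081/0.02205 - 1.96 = 1.713; power 95.7%.
- MBS freedom: SE = sqrt[(0.2410 + 0.2180)/630] = 0.02699; 0.084/0.02699 - 1.96 = 1.152; power 87.5%.
- Joint, as a product: 0.9567 x 0.8754 = 83.7%.

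These match the stated 95.7%, 87.5% and about 84%.

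**Adding a predose-pain stratum.** Let q be the share of severe attacks and g the response rate in moderate minus that in severe attacks, equal in both arms, with overall rates held at the protocol values. Stratifying replaces p(1-p) in each arm by p(1-p) - q(1-q)g^2. The documents give neither q nor g, so I assume q = 20-50% and g = 5-20 points.

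Middle case, q = 0.35 and g = 0.10: q(1-q)g^2 = 0.002275 per arm.
- Pain freedom: SE = sqrt[(0.30638 - 0.00455)/630] = 0.02189; power 95.9%.
- MBS freedom: SE = sqrt[(0.45893 - 0.00455)/630] = 0.02686; power 87.9%.

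| Severe share, gap | Pain freedom | MBS freedom | Joint (product) |
|---|---|---|---|
| Planned analysis | 95.7% | 87.5% | 83.7% |
| 20%, 5 points | 95.7% | 87.6% | 83.8% |
| 35%, 10 points | 95.9% | 87.9% | 84.3% |
| 35%, 20 points | 96.6% | 88.8% | 85.8% |
| 50%, 20 points | 96.7% | 88.9% | 86.0% |

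The combination of 20% severe and a 20-point gap is impossible for pain freedom: the placebo rate in severe attacks would be 15.1 - 0.8 x 20 = -0.9%. Over the feasible grid the variance falls by 0.3-6.5% for pain freedom and 0.2-4.4% for MBS freedom. If only pain freedom benefits, joint power at the top of the range is 0.9671 x 0.8754 = 84.7%, a rise of 0.9 points.

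**Chance imbalance.** The SD of the between-arm difference in severe share is sqrt[2q(1-q)/630], or 2.3-2.8 points, with 95% limits of 4.4-5.5 points either way. Multiplying the limits by the gap, the treatment difference could shift by 0.2-1.1 points, against planned effects of 8.1 and 8.4 points.

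**Validity.** In simulation (40,000 trials per setting) the country/region-only analysis rejected in 4.9-5.1% of null trials, and its mean error was below 0.03 points. At 35% severe and a 20-point gap, adding the stratum moved simulated power from 95.7% to 96.7% for pain freedom and from 87.5% to 88.6% for MBS freedom, in line with the formula.

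**Function endpoints.** The documents give no function response rates and no distribution of disability at dosing, so no gain can be calculated.

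**The case against.** The strongest reply is that nothing is broken. The method was fixed in the protocol, the test is valid, the stated power is reached without covariates, and the planned standard error already includes the variation from chance imbalance. All of that stands. A reader might infer that the planned estimate is biased or the trial underpowered; the documents and the calculation support neither.

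A reader might also borrow a generic baseline-to-outcome correlation of 0.5 and expect a much larger gain. That is out of reach here. With one-third of attacks severe and about 19% overall pain freedom, the correlation peaks when severe attacks never respond and moderate ones respond at 28.7%: 0.287 x sqrt(1/3 x 2/3)/sqrt(0.1915 x 0.8085) = 0.34. Being listed as a possible imputation covariate is not evidence of strong prognosis.

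Three further objections limit the remedy:
- Pain at dosing is not the baseline of MBS freedom. That baseline is the chosen symptom, so for this endpoint pain is only a prognostic covariate.
- Participants who had mistakenly dosed already report their time-of-dosing levels afterwards (SAP 5.2.5), so their stratum could be coloured by response. Their number is unknown.
- Changing the primary analysis may need a protocol amendment (Protocol 9) for a gain of perhaps one point of power.

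The objection that predose values are already used through the EAS and function populations is correct but incomplete: the spread within those populations stays unadjusted.

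**Conclusion.** The point holds as a modest improvement. The comparisons leave out a plausible prognostic variable that is already collected and, for pain, complete in the EAS. Under the stated assumptions joint co-primary power rises by between 0.1 and 2.3 points, with 0.6 in the middle case; without a benefit for MBS freedom the rise is at most 0.9. A chance imbalance in severity could move the estimate by up to about 1.1 points at its 95% limit.

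These figures rest on an assumed severe share, an assumed gap equal in both arms, the same gap for both endpoints in the joint range, and independence of the two tests. The function key secondaries might gain more, since disability at dosing has three levels, but the documents cannot show it.

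**What to change.** Before unblinding, in SAP 5.2.2, 6.1 and 6.2 and Appendix 1:
- For pain freedom and the pain key secondaries, stratify the Mantel-Haenszel risk difference by country/region and pain at dosing (moderate, severe). With the three regions in SAP 6.4 this gives 3 x 2 = 6 strata.
- For the return-to-function key secondaries, stratify by country/region and disability level at dosing, with a prespecified rule for merging sparse levels.
- For MBS freedom, either describe pain at dosing as a prognostic covariate or use the predose intensity of the chosen symptom.
- State a rule for values reported retrospectively after mistaken dosing, for example a separate stratum or a sensitivity analysis excluding these participants. SAP 5.2.5 does not collect MBS from them retrospectively, so a stratum based on the chosen symptom needs its own provision.
- Keep the country/region-only analysis as a sensitivity analysis.

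If the sponsor does not wish to amend Protocol 9.3.2.1, leave the main analysis as it is and prespecify the adjusted one as supportive.

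The cost is SAP wording, possibly a protocol amendment, and a few small strata for the function endpoints. No new data are needed.

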### **6.3. Assignment to Study Intervention**

Allocation of participants to treatment groups will proceed through the use of an IRT system. The site personnel (study coordinator or specified designee) will be required to enter or select information including but not limited to the user's ID and password, the protocol number, and the participant number. The site personnel will then be provided with a randomization number corresponding to the assigned treatment group, and DU or container number(s) when study intervention is being supplied via the IRT system. The IRT system will provide a confirmation report containing the participant number, randomization number, and DU or container number assigned. The confirmation report must be stored in the site's files.

Randomization will occur in the IRT. Randomization will be stratified by the use of stable prophylactic migraine medications through randomization (yes or no) and country/region.

Study intervention will be dispensed at the Baseline Visit as indicated in the [SoA](#).

The study-specific IRT reference manual and IPM will provide the contact information and further details on the use of the IRT system.

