#### 9.3.2. Primary Endpoint(s)/Estimand(s) Analysis

##### 9.3.2.1. Main Analytical Approach

Zavegepant will be tested for superiority against placebo at an  $\alpha=0.05$  level for both co-primary endpoints using the EAS. For each endpoint, treatment groups will be compared using a CMH test for the difference in percentages of participants achieving the endpoint response criteria (zavegepant-placebo) stratified by country/region. The stratified difference in percentages between treatment groups will be presented with p-value and a 95% CI based on normal approximation. For individual treatment group, the percentage of participants achieving the endpoint response criteria will be presented with a 95% CI based on normal approximation.

Participants with missing data at 2 hours postdose or taking rescue medication at or before 2 hours postdose will be classified as failures.

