### 5.2.2. Analyses for Categorical Endpoints

Categorical variables will be summarized as the number and percentage of participants within each category. Percentages in frequency tables are calculated against the number of participants in each treatment group in the specified analysis set. For each endpoint, Mantel-Haenszel risk estimation will be used for the difference in percentages of participants achieving the endpoint response criteria (zavegepant-placebo) stratified by country/region. The difference in percentages between treatment groups will be presented with p-value and asymptotic standard error (ASE) together with a 95% CI based on normal approximation. For individual treatment group, the percentage of participants achieving the endpoint response criteria will be presented with ASE and a 95% CI based on normal approximation.

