#### 6.4. Subset Analyses

For the co-primary and key secondary endpoints, subgroup analyses will be conducted for the following baseline demographic and characteristic variables:

- Country/region at randomization: China, Korea, Taiwan
- Age at informed consent category 1: <40, ≥ 40

- Sex: male, female
- BMI category:  $<25 \text{ kg/m}^2$ ,  $\geq 25$  to  $<30 \text{ kg/m}^2$ ,  $\geq 30 \text{ kg/m}^2$
- Aura on study before dosing: yes, no
- History of migraine with aura: yes, no (see Section 6.5.1.2)
- Historical number of moderate to severe migraine attacks per month:  $<4$ ,  $\geq 4$  (overall median)
- Stable prophylactic migraine medication use through randomization: yes, no.

For the primary endpoint of “percentage of participants with an MBS reported before dosing that is absent at 2 hours postdose”, the following characteristic variables will additionally be used for subgroup analysis:

- MBS on study before dosing: Nausea
- MBS on study before dosing: Phonophobia
- MBS on study before dosing: Photophobia

Main analysis method described in Section 5.2.2 will be used, except for the subgroup analysis by country/region at randomization, in which Mantel-Haenszel risk estimation without stratification will be conducted.

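### The co-primary and key secondary analyses stratify by country/region only and leave out the second randomization factor, prophylactic medication use; the effect is small and conservative, and cheap to correct.

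*SAP*

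**What the plan says.** **Randomization.** Protocol 6.3 names two factors: "Randomization will be stratified by the use of stable prophylactic migraine medications through randomization (yes or no) and country/region". The synopsis and the schedule of activities say the same.

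**Main analysis.** Protocol 9.3.2.1 specifies a "CMH test for the difference in percentages of participants achieving the endpoint response criteria (zavegepant-placebo) stratified by country/region". SAP 5.2.2 turns this into a Mantel-Haenszel estimate of "the difference in percentages of participants achieving the endpoint response criteria (zavegepant-placebo) stratified by country/region". SAP 6.1.1.1 applies it to pain freedom: "The Mantel-Haenszel risk estimation stratified by country/region will be used". SAP 6.1.2.1 (MBS freedom), 6.2.1 to 6.2.8 (the eight key secondary endpoints) and Appendix 1 follow the same pattern. Protocol 9.1 and SAP 5.1 state the hypotheses in terms of a stratified response rate without naming the strata.

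**Where prophylaxis use does appear.** It is a baseline variable in SAP 3.4 and a subgroup in SAP 6.4 ("Stable prophylactic migraine medication use through randomization: yes, no"). It is not among the imputation covariates listed for pain freedom in SAP 5.3. The sensitivity analyses in Protocol 9.3.2.2 and SAP 6.1 concern missing data only. Neither document explains why the factor is left out of the main analysis.

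**The concern.** Stratified randomization forces the arms to be balanced on the stratifying factor. If that factor predicts response, the treatment difference varies less from trial to trial than a variance formula that ignores the factor assumes. The reported standard error is then too large, the CI a little wide and the p-value a little high.

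What is at stake is a small amount of power. It counts because both co-primary endpoints must be significant at 0.05, MBS freedom is the weaker of the two, and eight key secondary endpoints follow in fixed sequence, each tested only if the one before it succeeded.

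**Working it through.** **Inputs from Protocol 9.5.** 630 evaluable participants per arm; pain freedom 23.2% vs 15.1%; MBS freedom 40.5% vs 32.1%; 2-sided alpha 0.05. SAP 6.4 gives three levels for the other factor ("Country/region at randomization: China, Korea, Taiwan"), so both factors together make 3 x 2 = 6 strata.

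**Inputs that are assumed.** The documents do not give the share of prophylaxis users, f, or the response gap between users and non-users, g. I take f = 10-30% and g = 5-10 points, the same gap in both arms, with a constant treatment difference.

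**Step 1: reproduce the stated power.** Power = Phi(d/SE - 1.96), with SE = sqrt{[p1(1-p1) + p2(1-p2)]/630}.
- Pain: variance sum 0.1782 + 0.1282 = 0.3064; SE = 0.02205; 0.081/0.02205 - 1.96 = 1.71; power 95.67% (stated 95.7%).
- MBS: variance sum 0.2410 + 0.2180 = 0.4589; SE = 0.02699; 0.084/0.02699 - 1.96 = 1.15; power 87.54% (stated 87.5%).
- Joint, assuming independence: 0.957 x 0.875 = 83.7% (stated about 84%).

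The stated figures reproduce with no stratification at all, so none of them depends on the omitted factor.

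**Step 2: condition on prophylaxis use.** The within-stratum variance in each arm is p(1-p) - f(1-f)g^2. The variance sum therefore falls by 2f(1-f)g^2.

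| f, g | 2f(1-f)g^2 | Pain: reduction, power | MBS: reduction, power | Joint |
|---|---|---|---|---|
| 10%, 5 points | 0.00045 | 0.15%, 95.69% | 0.10%, 87.57% | 83.8% |
| 30%, 10 points | 0.0042 | 1.37%, 95.89% | 0.92%, 87.83% | 84.2% |

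Widening the assumptions to 5-30% users and gaps of 5-15 points takes joint power only as far as 84.8%. With g = 0 nothing changes.

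**Step 3: allow for the balance already achieved.** Step 2 slightly flatters the change. Because randomization balances the factor, the country-only estimate already has the smaller true SD and only its estimated SE is too large. Its actual power is Phi[(d - 1.96 x SE0)/SE1], where SE0 ignores the factor and SE1 allows for it. For MBS at f = 30%, g = 10 points: (0.084 - 1.96 x 0.02699)/0.02687 = 1.157, or 87.6%, against 87.8% with both factors. The gain is about 0.2 points, not 0.3.

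**Step 4: simulation.** Trials were simulated with assumed country shares of 70/20/10 and randomization balanced on both factors, comparing country-only with both-factor Mantel-Haenszel analyses.
- The true SD of the two estimates was the same. The estimated SE fell, for example from 0.02203 to 0.02191 for pain freedom at f = 20%, g = 10 points.
- MBS power rose by 0.02 to 0.15 points within the assumed range (87.48% to 87.63% at f = 30%, g = 10 points).
- Type I error, with gaps of 10 to 15 points, was 4.6-5.0% for country only and 5.0-5.1% for both factors.

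**The case against.** The strongest reply is that little is lost. Protocol and SAP agree on country/region alone, so the analysis is prespecified and there is no conflict between the documents. The test is valid, and any error is on the safe side. The benefit rests on a user share and a response gap that appear nowhere in the documents. The factor is also not thrown away: it balances the arms and is a prespecified subgroup. All of this stands, and it limits the point to a small improvement.

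Sparse strata are a fair practical objection. If one country/region contributes 10% of participants and 10% of them use prophylaxis, that stratum holds 1260 x 0.10 x 0.10, or about 13 people, and fewer still for the key secondary endpoints restricted to participants with functional disability. A rule triggered only by an empty arm would not deal with such strata.

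A reader might infer three stronger things that the documents do not support:
- **That type I error is inflated or the power statement is wrong.** Steps 1 and 4 show neither.
- **That a real gain in precision is being forgone.** The spread of the estimate is the same either way; what changes is whether the standard error reports it correctly.
- **That pre-dose pain severity should be a stratum too.** It is not a randomization factor. SAP 5.3 offers it only as a possible covariate in a sensitivity imputation for pain freedom. Under SAP 5.2.5 it is recorded retrospectively for participants who had mistakenly already dosed. Adding it would also split strata that may already be small.

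**Conclusion.** The mismatch is plain in the documents: two randomization factors, one analysis factor, no stated reason and no supporting analysis with both. Its consequence is a standard error that is slightly too large if prophylaxis use is prognostic. Under the assumed 10-30% users and 5-10 point gap, the usual power formula moves MBS freedom from 87.5% to about 87.6-87.8% and pain freedom from 95.7% to about 95.7-95.9%. Allowing for the balance already achieved makes the difference a little smaller, and it is nil if the factor is not prognostic. The case for change is therefore not the size of the gain. Analysing by the randomization strata makes the standard error match the design at almost no cost.

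**What to change.** Before unblinding, in SAP 5.2.2, 6.1, 6.2.1 to 6.2.8 and Appendix 1:
- Stratify the Mantel-Haenszel estimate, CI and p-value for the co-primary and key secondary endpoints by country/region x prophylactic medication use (six strata).
- Use the prophylaxis value recorded in the IRT at randomization, and say so, because SAP 6.5.1.5 also carries a definition based on medication dates.
- Prespecify that the two prophylaxis strata within a country/region are collapsed when a stratum is empty or very small in either arm, and give the minimum count.
- Do not add pre-dose pain severity as a stratum.

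Record the change in SAP 2.1, which currently lists no modifications. The opening of Protocol section 9 requires major modifications of the primary analyses to be reflected in a protocol amendment, so the sponsor should decide and document whether this one is major.

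The programming cost is one extra stratification variable and the collapsing rule; an amendment, if needed, would be the larger cost. If the sponsor prefers to keep country/region alone, the minimum is to state why and to prespecify the six-stratum analysis as a sensitivity analysis of both co-primary endpoints.
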